#### E. Data and Safety Monitoring Plan

1. Deidentified data from the published primary study will be utilized for the post hoc analysis.

#### F. Timepoints of Data Collection

[figure not shown]
1. Data variables included in the analysis:
  - I. Procedure costs and related costs; related CPT codes
  - II. SF-36 (pre-op, 3 months, 6 months, and 1 years)
  - III. EQ5D (pre-op, 3 months, 6 months, and 1 years)
  - IV. Neck pain disability index (pre-op, 3 months, 6 months, and 1 years)
  - V. Baseline Demographics
  - VI. MJOA (pre-op, 3 months, 6 months, and 1 years)
  - VII. Return to Work Status 1 Month, 3 Months, 6 Months, 1 Year
  - VIII. Health Resource Utilization Diary (1 month, 3 months, 6 months, 1 year)
  - IX. Inpatient Hospital and Rehabilitation Utilization Data
  - X. Hospital-specific and year-specific Medicare cost-to-charge ratios
  
2. Study Endpoints
  - I. The primary endpoint will be the cost-effectiveness comparison between ventral and dorsal surgery in CSM.

II. The secondary endpoint will be the cost-effectiveness comparison between dorsal cervical fusion and laminoplasty

[figure not shown]
3. Data Timepoints

- I. Preop: SF36, EQ5D, neck pain disability index
- II. Procedure: related hospital costs, hospital-specific and year-specific Medicare cost-to-charge ratio
- III. 1 month: Complications and related costs (if applicable), health resource utilization diary, Return to Work Status
- IV. 3 months: SF36, EQ5D, neck pain disability index, health resource utilization diary, Return to Work Status
- V. 6 months: SF36, EQ5D, neck pain disability index, health resource utilization diary, Return to Work Status
- VI. 1 year: SF36, EQ5D, neck pain disability index, health resource utilization diary, Return to Work Status

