## DESCRIPTION OF STUDY

### A. Purpose

1. To determine if ventral surgery is more cost-effective compared to dorsal (fusion or laminoplasty) surgery.
2. To determine the relative cost-effectiveness between anterior cervical discectomy and fusion (ACDF), posterior cervical fusion (PCF), and cervical laminoplasty.

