### A. Background

This study aims to compare the cost of care of anterior versus posterior surgical approaches for the management of Cervical Spondylotic Myelopathy (CSM). Due to the significant gap in today's literature, we aim to conduct a post hoc analysis of data from the randomized trial "Cervical Spondylotic Myelopathy Surgical Trial" ([www.ClinicalTrials.gov](http://www.ClinicalTrials.gov); identifier: NCT02076113; LCID# 2013-085) to determine the cost effectiveness of various procedures as related to the management of CSM. Specifically, we aim to compare 1) the cost effectiveness of ventral surgery versus dorsal (fusion or laminoplasty) surgery; and 2) to determine the relative cost-effectiveness between anterior cervical discectomy with fusion (ACDF), posterior cervical fusion (PCF), and cervical laminoplasty.

The aforementioned study that the proposed analysis is based on was conducted in collaboration between multiple academic institutions in North America. The resulting clinical and patient-reported outcomes from the CSM-S RCT suggested similar effectiveness in both anterior and posterior surgical approaches. Of note, the study showed that cervical laminoplasty, a relatively low instrumentation-related cost procedure, was effective in managing CSM. The findings of the proposed analysis will offer further consideration on patient financial burdens as related to CSM management to better improve related clinical decision-making for both patients and their providers.

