### D. Research Plan

1. Post hoc analysis will be conducted on the following data that were collected during the trial (LCID#2013-085) The study flow schema is outlined in Figure 1
  1. Our post hoc study will utilize the health resource information, well-known quantitative scales to measure functional outcomes (SF-36, Oswestry Neck, mJOA, and EuroQol-5D taken at pre-op, 3 months, 6 months, 1 year, 2 years, 3 years, 4 years, and 5 years), costs related and incidence of re-operations and complications at 30 days and 1 year after surgery to compare the costs related to each procedure: comparing the cost effectiveness of ventral surgery versus dorsal (fusion or laminoplasty) surgery and comparing the relative cost-effectiveness between anterior cervical discectomy with fusion (ACDF), posterior cervical fusion (PCF), and cervical laminoplasty. Quality of life measures (I.e. SF-36 as one overall score per timepoint) will be utilized to determine patient satisfaction with the procedure of choice and subsequently create a comprehensive snapshot for clinical decision making. Utilization of quality-of-life scales will help relate success of the procedure as deemed by the patient in relation to the related costs.
  2. Health resource utilization information was collected using patient diaries along with copies of all medical bills and receipts at 1 month, 3 months, 6 months, and 12 months post-operatively for all patients. Participants were asked to monitor days missed from work and days unable to perform usual activities, in addition to days missed from work for medical treatments or evaluations.
2. The overall cost will be estimated for each patient from a societal perspective and will include the following components:
  - I. *Index Hospitalization Cost – performed on all patients:*
    - Hospital Costs: Total hospital charges (Total HC) will be used to estimate costs using hospital-specific and year-specific Medicare cost-to-charge ratios (CCR). The costs will be adjusted for inflation to the latest year of the study (2018) without a 3% discount. – *Assumptions:* cost-to-charge ratios for all hospitals and all relevant years will be provided. Data will be complete for all patients from all sites.

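### Does the secondary endpoint leave out two of the comparisons that the protocol sets as aims?

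*Protocol*

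**What the plan says.** Section A, Purpose, has two items. The first is "To determine if ventral surgery is more cost-effective compared to dorsal (fusion or laminoplasty) surgery". The second is "To determine the relative cost-effectiveness between anterior cervical discectomy and fusion (ACDF), posterior cervical fusion (PCF), and cervical laminoplasty". The Background repeats the second aim almost word for word, and the Research Plan (section D, item 1.1) lists it among the analyses to be done: "comparing the relative cost-effectiveness between anterior cervical discectomy with fusion (ACDF), posterior cervical fusion (PCF), and cervical laminoplasty".

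Section F, item 2, lists two endpoints. Item 2.I reads "The primary endpoint will be the cost-effectiveness comparison between ventral and dorsal surgery in CSM". Item 2.II reads "The secondary endpoint will be the cost-effectiveness comparison between dorsal cervical fusion and laminoplasty". ACDF does not appear by name in either. Section E confirms that the work uses existing data: "Deidentified data from the published primary study will be utilized for the post hoc analysis".

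**The concern.** Three places in the protocol state a three-procedure aim, and the one place that ranks endpoints states a two-procedure one. The primary endpoint does not obviously fill the gap, because Purpose item 1 defines dorsal surgery as fusion or laminoplasty. A comparison of ventral surgery with that pooled group does not by itself say how ACDF stands against either dorsal procedure.

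The setting adds some weight. The analysis is post hoc on a published trial, and the Background already reports that outcomes "suggested similar effectiveness in both anterior and posterior surgical approaches" and describes laminoplasty as effective with relatively low instrumentation cost. If the status of the two ACDF comparisons is open, they could be headlined as a stated aim or set aside as non-endpoints once the costs are known. Pre-labelling comparisons is a reasonable safeguard against that.

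**Working it through.** The protocol gives no sample size, alpha, power or cost figure that bears on this, so the check is a comparison of texts plus a short identity.

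**1. Count of comparisons**

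- Purpose item 1: ventral versus pooled dorsal, 1 comparison.
- Purpose item 2: three procedures, read as pairs, C(3,2) = 3 comparisons.
- Total stated: 1 + 3 = 4.
- Endpoints: 2.I covers 1 and 2.II covers 1, so 2 of 4 have endpoint status.
- Without it: ACDF versus posterior fusion and ACDF versus laminoplasty, which are 2 of 4 overall and 2 of the 3 in Purpose item 2.

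The expansion into three pairs is an interpretation. The text speaks of relative cost-effectiveness between three procedures and does not list pairs.

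**2. Is the analysis planned?**

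| Place | Three procedures compared? |
|---|---|
| Purpose, item 2 | Yes |
| Background | Yes |
| Research Plan, item 1.1 | Yes |
| Study Endpoints, 2.II | Two of the three |

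The Research Plan is the operative section for what will be computed, and it includes ACDF. An analyst would have to disregard three sections to leave the ACDF comparisons out.

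**3. Is their status undefined?**

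Section F labels one endpoint primary and one secondary. By the usual convention, a planned comparison that is on neither line is not a secondary endpoint. The protocol does not say this in words, but the default reading is available.

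**4. Do the two endpoints carry the missing information?**

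Assume that ventral surgery and ACDF are the same group. The text does not settle this, and the figures are not shown. Let V, P and L be the mean cost (or mean effect) for ACDF, posterior fusion and laminoplasty, and let p be the known share of fusion in the dorsal group.

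- Endpoint 2.I estimates D1 = V − [pP + (1 − p)L].
- Endpoint 2.II estimates D2 = P − L.
- Since pP + (1 − p)L = L + pD2, it follows that V − L = D1 + pD2.
- Subtracting D2 gives V − P = D1 − (1 − p)D2.

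Three groups have two independent differences, and the two endpoints are such a pair. A pooled result can hide opposite answers: with D1 = 0, V − L = pD2 and V − P = −(1 − p)D2, which differ in sign. But D2 is the secondary endpoint, so that situation would show in the endpoint results. The identity holds for unadjusted mean differences. It does not supply intervals, and it does not carry over to ratios directly.

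**The case for a change.** The best case for a change is that endpoint ranking is protocol content, not detail for the statistical analysis plan. This protocol does rank its endpoints, and the ranking disagrees with its own aims. Whoever writes the analysis plan inherits the disagreement and must pick a side. The cure is one sentence, either extending 2.II to ACDF or calling the two ACDF comparisons exploratory, and it needs no new data. In a post hoc analysis with effectiveness results already known, even a small freedom over emphasis is better removed.

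The textual part of this stands: the sections do not match, and a careful author would have made them do so. The argument about selective emphasis is weaker than it looks. The three-procedure comparison is stated in advance three times, so dropping an ACDF result would be plain to anyone holding the protocol. The known results in the Background concern effectiveness and instrumentation cost, not the total societal cost that this study will estimate. A further step would be to fix how the three options are ordered, how dominated options are handled and how intervals are given, but that goes beyond a labelling mismatch and is commonly left to the analysis plan.

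**Conclusion.** No change follows. The endpoint list is narrower than the aims by two comparisons out of four, but both are already in the Research Plan and can be made with the same data. The document sets no alpha, so no error-rate consequence arises, and it gives no costs, so no effect on a result can be claimed. What remains is a label, secondary or exploratory, with an ordinary default under the ranking in section F.

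This conclusion rests on the analyst following the Research Plan as well as the endpoint list. It does not depend on ventral surgery and ACDF being the same group. If they are the same, the two endpoints together determine the unadjusted pairwise mean differences. If they are not, ACDF is absent from the endpoints, but the Research Plan still commits to comparing it with both dorsal procedures.

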**Figure 1: Cervical Spondylotic Myelopathy Trial Study Flow Schema from CSM Trial**

**Figure 2:** Flow of Participants in the Cervical Spondylotic Myelopathy Surgical Trial

